Each participant will be provided two 30mL bottles (2000mg CBD per bottle) with a syringe dropper during their initial (baseline) visit with instructions/demonstration to administer the solution under the tongue (0.5 cc ~1/2 dropper) twice per day (BID) 8-12 hours apart (morning and evening) at the prescribed daily dosage (63mg/day). The sublingual route of administration allows the product to be absorbed directly into venous circulation, and thus bypasses the liver and eliminates the consequences of first pass metabolism; ultimately increasing its bio-availability. The bioavailability of CBD administered orally (including sublingual) is estimated to be 13-19% and its half-life estimated to be around 18-32 hours.

Physical Discomforts and Intervention Risks:

In previous clinical trials using hemp-derived products administered orally (liquid or capsule) and swallowed, a small percentage of patients experienced tiredness, change in appetite and gastro-intestinal discomfort following ingestion. We will be using daily doses of hemp extract that are considerably lower than the daily doses used in the clinical trials. Therefore, the chance of our participants experiencing these side effects is minimal.

Occasionally one or more of the following potential side effects of taking blood samples may occur: pain, bruising, slight bleeding, light-headedness, fainting and (rarely) an infection. A trained technician will be drawing the blood.

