Safety Monitoring and Stopping Criteria: Safety monitoring will occur during the initial baseline visit as well as throughout the participant's duration in the study, including a 1week follow-up contact after study termination. As noted below, the baseline assessment conducted during the first visit will include a brief physical exam (including vital signs) and a thorough medical and psychiatric history, including a review of past medical history, concomitant medications, inclusion/exclusion criteria, and potential contraindications. Safety monitoring will include active and passive surveillance procedures using preexisting safety monitoring guidelines. Participants will be assessed actively at each laboratory visit by study personnel using the side effects/adverse events checklist. Each participant will be read each side effect/adverse event from the checklist and instructed to self-report as yes (go) or no (no go). If a participant experiences any of the side effects/adverse events from the checklist provided at the baseline visit, study personnel will then contact the study physician ([name]) for consultation. The side effects/adverse events will be triaged as mild, moderate or severe, and a determination will be made by the study physician as to whether the side effect/adverse event is due to the investigational test article or some other circumstance (e.g. food poisoning). If the reaction or event is determined to be due to the investigational test article and graded moderate to severe by the study physician, the participant will then be instructed to stop participation and advised to seek medical care by their primary physician or hospital. (Refer to stopping

criteria below). Any serious adverse reaction or event will be followed until full resolution. All adverse reactions and events will be reported to the UF IRB within 24-48-hrs and documented in the participant's file (redcap). The PI/physician decides that the participant should be withdrawn for **safety reasons** (presence of active lesions in the oral cavity/sublingual region or suffering side effects or adverse events associated with the use of the investigational product). List of side effects and adverse reactions are listed below*

Stopping Criteria:

- 1. Participant is unwilling to continue in the study.
- 2. Lack of compliance with protocol.
- 3. Investigator or study sponsor stops the study for any reason.

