- 4. Participant is enrolled in error or lost to follow-up (lost to follow-up will be defined as a subject failing to attend planned study visits or failure to respond to contacts by study personnel after documented 2 attempts).

*Potential Side Effects and/or Adverse Events (AEs):

- 1. Feelings of anxiety (nervousness, restlessness or being tense, feelings of danger, panic, or dread), paranoia, or negative mood (depression or suicidal thoughts), or paranoia.
- 2. Suicidal ideation
- 3. Poor quality of sleep (persistent insomnia).
- 4. Feelings of extreme fatigue, sleepiness or drowsiness.
- 5. Feelings of nausea (upset stomach, vomiting or gastro-intestinal (GI) distress (e.g. diarrhea).
- 6. Change in or loss of appetite.
- 7. Feelings of light-headedness or dizziness.
- 8. Visual disturbances such as blurry/double vision.
- 9. Hypotension, hypertension, tachycardia, heart palpitations, syncope or dyspnea.
- 10. Development of a skin rash with redness and itching.

Each participant will be provided a detailed safety monitoring checklist of side effects and/or adverse reactions that they may potentially experience from ingesting the investigational product. Suicidal thoughts are not expected to be common, and there is no evidence that we know of about any association of CBD to suicide. In the unlikely event that a research participant would indicate suicidal thoughts or ideation during the visits or phone calls, they will be immediately interviewed for a formal assessment by [name] or Research Coordinator [name] (both are trained to perform such an assessment). If the assessment finds out they are not seriously suicidal, they can continue in the study. Reversely, if we the assessment finds the patient is serious about their intentions, we will either call 911 or have them agree to go to an ER for evaluation. The patient will be asked to to stop assuming CBD. In that case, we will continue to follow them if we do refer them somewhere. At the end of the study, we will try to assess whether there is any possibility that the CBD product itself is associated with the suicidal thinking or behavior.

[figure not shown]

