Participants will then be instructed on how to perform their own passive surveillance for identifying these side effects/adverse events and what to do if they experience any of them between study visits while they are ingesting the investigational product. Each participant will be provided a daily log chart to record their daily CBD doses for compliance and monitoring purposes. During the passive surveillance period participants will be instructed to contact study personnel if they experience any of the side effects/adverse events from the checklist provided at the baseline visit. Study personnel will then contact the study physician ([name]) for consultation. The side effects/adverse reactions will be triaged as mild, moderate or severe, and a determination will be made as to whether the side effect/adverse reaction is due to the investigational product or some other circumstance (e.g. food poisoning). If the event is determined to be due to the investigational product and graded moderate to severe by the study physician, the participant will then be instructed to stop participation and seek medical care by their primary physician or hospital. Any participant that reports a serious adverse event will be followed to full resolution.

Patients will be contacted weekly and asked about missing doses. We will take note of any missed dose. Approximately at days 15 and 45, patients will be asked to provide a picture, sent via text to the study phone, with a close up of their CDB bottles, so that we can verify the liquid level. Patients will be instructed to not include anything identifiable in the background. Patients will be also instructed to bring their CBD bottles at every visit after the first. In case of non compliance (e.g., the patient forgets to bring the bottle or does not send the picture), the PI will consider whether to withdraw the patient for the study.

Study personnel will perform a follow-up phone call at 1 week after completion from the study for continued safety monitoring. Study personnel will refer to the checklist to determine if the participant has experienced or is experiencing any side effects or adverse events using the safety monitoring guidelines. If the participant reports experiencing any of the side effects/adverse events from the checklist the study physician will be consulted immediately for guidance and the participant's condition will be followed until full resolution.

Experimental Procedures:

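### Checklist item 4 puts the word *extreme* inside a yes/no screening question that comes before severity grading, so ordinary tiredness may go unrecorded

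*Combined protocol and SAP*

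**What the plan says.** All of this is in section 6, Research Plan.

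- **Known effects** (Physical Discomforts and Intervention Risks). In earlier trials, "a small percentage of patients experienced tiredness, change in appetite and gastro-intestinal discomfort following ingestion". The planned doses are described as considerably lower, and the text concludes: "Therefore, the chance of our participants experiencing these side effects is minimal".
- **Screening** (Safety Monitoring and Stopping Criteria). At laboratory visits, "Each participant will be read each side effect/adverse event from the checklist and instructed to self-report as yes (go) or no (no go").
- **Trigger and grading** (same heading). The study physician is contacted "If a participant experiences any of the side effects/adverse events from the checklist provided at the baseline visit". After that step, "The side effects/adverse events will be triaged as mild, moderate or severe".
- **Between visits** (the surveillance text after the list of side effects). Here "participants will be instructed to contact study personnel if they experience any of the side effects/adverse events from the checklist", and the same three-level triage follows. The 1-week follow-up call also works from the checklist.
- **The list** (Potential Side Effects and/or Adverse Events). Item 4 is "Feelings of extreme fatigue, sleepiness or drowsiness". Item 3 is "Poor quality of sleep (persistent insomnia"). Item 5 (nausea and gastro-intestinal distress) and item 6 (appetite) contain no severity word.

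**The concern.** The plan separates two tasks. The participant says whether an effect is present, and the effect is then triaged for severity, with the study physician's grade deciding what follows. Item 4 mixes the two. It asks the participant to apply a severity threshold while answering yes or no, before anyone has graded anything. That fits poorly with a scale whose lowest grade is mild.

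Two things are at stake. First, a participant who is clearly but not extremely fatigued can truthfully answer no, in which case the checklist prompts no call to the physician. Product-related events graded moderate to severe lead to action under the protocol, so a missed yes also determines whether that pathway is ever reached. Second, sections 5 and 7 present the pilot as groundwork for a larger study. A low tiredness count could mean that the product seldom causes tiredness, or that the question filtered it out. The data could not tell these apart.

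**Working it through.** The plan has no figure to reproduce here. The check is a comparison of the texts.

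**Step 1. Match each known effect to its checklist item.**

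| Effect named from earlier trials | Item | Severity word in the item |
|---|---|---|
| Tiredness | 4 | *extreme* |
| Appetite change | 6 | none |
| Gastro-intestinal discomfort | 5 | none |

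Only tiredness is screened through a severity word.

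**Step 2. Take both grammatical readings of item 4.**

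- Reading A: *extreme* governs fatigue, sleepiness and drowsiness. Ordinary tiredness of any kind is a literal no.
- Reading B: *extreme* governs fatigue only. Ordinary sleepiness or drowsiness is a yes and goes to triage. Ordinary fatigue without sleepiness is a literal no.

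The text does not settle which is meant. Ordinary fatigue without sleepiness is screened out under both.

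**Step 3. Look for another route that would elicit such an event.** No open-ended adverse-event question is described. The weekly contacts are stated to ask about missed doses. The sleep questionnaire (PSQI) is given at all three visits as an outcome measure and is not tied to adverse-event triage. The rule that all adverse reactions and events go to the IRB within 24-48 hours governs events already known to staff and does not elicit them. An unprompted report remains possible, although between visits participants are told to call about checklist effects.

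**Step 4. Size.** The documents give no incidence of tiredness and no severity split, so no estimate can be made. An illustration needs assumed inputs: true tiredness q of 10-30%, a share s of 10-20% that the participant would call extreme, and the planned n of 5 to 7. It also assumes Reading A, fully literal answers and no unprompted reports.

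- All grades counted: P(at least one case) = 1 - (1 - q)^n.
  - n = 7: 1 - 0.90^7 = 52% to 1 - 0.70^7 = 92%.
  - n = 5: 1 - 0.90^5 = 41% to 1 - 0.70^5 = 83%.
- Extreme only: P(at least one case) = 1 - (1 - qs)^n, with qs from 0.10 x 0.10 = 0.01 to 0.30 x 0.20 = 0.06.
  - n = 7: 1 - 0.99^7 = 7% to 1 - 0.94^7 = 35%.
  - n = 5: 1 - 0.99^5 = 5% to 1 - 0.94^5 = 27%.

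This is the strictest case. Under Reading B the loss is smaller, and it could be nil if everyone who is tired is also sleepy or reports unprompted.

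**The case against.** The strongest reply is that the text supports much less than it first suggests. Several stronger inferences are tempting, and the documents do not bear them out.

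- *Mild and moderate tiredness can never be graded.* This does not follow. Under Reading B ordinary sleepiness is captured. Even under Reading A, *extreme* is the participant's word and the grade is assigned afterwards, so fatigue that a participant calls extreme may be graded moderate. Unprompted reports are also possible.
- *Tiredness is the effect the protocol expects first.* It is only named first in a list of three, with no order of likelihood, and the chance of all three is called minimal.
- *Item 3 screens out ordinary poor sleep in the same way.* Its main term, poor sleep quality, is unqualified, and the bracket may be an example or a gloss. Insomnia is not among the three effects named from earlier trials. At most this item needs clarifying.
- *The larger trial would inherit a falsely low rate.* No adverse-event rate is a stated outcome, and 5 to 7 uncontrolled participants give no usable rate under any wording. What can be said is that a low count would be uninterpretable.
- *The illustrative probabilities measure the loss.* They rest on assumed rates that sit uneasily with the protocol's description of a small percentage, and on the strictest reading.

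It is also fair to say that the handed-out checklist is described as detailed and may be worded differently, that a figure after the list is not reproduced, and that the pre-existing monitoring guidelines are not in the documents. These limit certainty. Still, the safety-monitoring text refers the reader to the printed list, and that list is the only wording available.

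What stands is the mismatch itself: a severity word ahead of a grading step, in one item, with ordinary fatigue excluded under either reading.

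**Conclusion.** The concern holds in limited form. Item 4 sets an ambiguous severity threshold before grading, and it does so for only one of the three side effects the protocol itself names. Ordinary fatigue without sleepiness is a literal no under either reading, and ordinary tiredness generally is a no under the stricter one. Such events may therefore not reach the physician or the record. The size of the loss is unknown and could be nil. The conclusion assumes that the printed list is the wording read to participants and that they answer it literally. This is a cheap improvement in safety ascertainment. It does not touch the primary gene-expression outcome.

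**What to change.** Delete *extreme* from item 4, for example: fatigue, tiredness, sleepiness or drowsiness. Leave severity to the mild/moderate/severe triage already in the plan. Use the same wording at the visits, for self-surveillance between visits and at the 1-week call, and check that the handed-out checklist matches. As a secondary clarification, state that the bracketed insomnia term in item 3 is an example and not a threshold.

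The cost is a reworded checklist and a minor amendment. More events will need triage and IRB reporting within 24-48 hours. Some may be graded moderate and, if judged product-related, enter the existing action pathway, which matters in a study of 5 to 7 people. The change leaves that pathway as it is and takes no position on it.

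### The protocol does not say whether its general adverse-event rule or its suicidality paragraph governs suicidal ideation, and the two differ on continuation and on when relatedness is judged

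*Combined protocol and SAP*

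**What the plan says.** All the relevant text is in Section 6, Research Plan.

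- **General rule, at visits** (Safety Monitoring and Stopping Criteria). For any checklist event, "study personnel will then contact the study physician". The event is given one of three severity grades. On relatedness the rule reads: "a determination will be made by the study physician as to whether the side effect/adverse event is due to the investigational test article". Where it is related and "graded moderate to severe by the study physician, the participant will then be instructed to stop participation". The reader is then referred to stopping criteria further down.
- **General rule, between visits** (the passive-surveillance paragraph before Experimental Procedures). The same steps are repeated. The physician grades the event. On relatedness the wording is "a determination will be made as to whether the side effect/adverse reaction is due to the investigational product", here without naming who makes that judgement.
- **Event list** (Potential Side Effects and/or Adverse Events). Suicidal thoughts are part of item 1, and suicidal ideation is item 2.
- **Suicidality paragraph** (directly after that list). A person whose name is removed, or the Research Coordinator, interviews the participant at once. Then: "If the assessment finds out they are not seriously suicidal, they can continue in the study". If intent is serious, the participant is sent for emergency evaluation, is asked to stop CBD, and is followed if referred. On whether the product played a part in the event, the paragraph says only: "At the end of the study, we will try to assess whether there is any possibility that the CBD product itself is associated".
- **Safety withdrawal** (an unnumbered sentence just above the Stopping Criteria list). The PI or physician may withdraw a participant for safety reasons, which include "suffering side effects or adverse events associated with the use of the investigational product".
- **Stopping Criteria.** There are four numbered items: unwillingness, "Lack of compliance with protocol", the study being stopped, and enrolment in error or loss to follow-up.

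**The concern.** Two rules cover the same event and turn on different facts. The general rule turns on grade and relatedness; the suicidality paragraph turns on seriousness of intent alone. Because the general rule makes stopping depend on relatedness, relatedness has to be judged when the event occurs. The suicidality paragraph mentions it only at the end of the study.

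The paragraph is the more specific text, so study staff may well follow it on its own. They could then keep on product a participant whom the general rule would stop. The assessment that decides continuation may be the Research Coordinator's, and the paragraph does not mention physician grading. This concerns participant safety at a moment when staff must act at once and have no time to interpret the protocol.

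A smaller fault lies next to it. The general rule refers to a list of stopping criteria that does not contain the criterion the reader has been sent to find.

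**Working it through.** No arithmetic applies: the point depends on no sample size, effect or error rate. The check sets the passages side by side.

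**Step 1: do both rules cover the event?** Yes. The general rule applies to any event on the checklist, at visits and between them. The printed list includes suicidal thoughts (item 1) and suicidal ideation (item 2). The suicidality paragraph applies to the same thoughts when reported at visits or by telephone. No sentence makes an exception to the general rule, gives one text precedence, or says that both apply.

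**Step 2: what does each rule turn on?**

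| Point | General rule | Suicidality paragraph |
|---|---|---|
| Test | Related to product, and moderate to severe | Serious intent or not |
| Relatedness judged | At triage, since stopping depends on it | At the end of the study |
| Consequence if met | Stop participation, seek care | Emergency evaluation, stop CBD, follow-up if referred |

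**Step 3: cross the two tests.** With two yes/no tests there are 2 × 2 = 4 cases.

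| Serious intent? | Related and moderate to severe? | General rule | Suicidality paragraph | Result |
|---|---|---|---|---|
| No | No | No required stop | May continue | Agree |
| No | Yes | Stop participation | May continue | Differ |
| Yes | No (e.g. judged unrelated) | No required stop | Stop CBD | Differ |
| Yes | Yes | Stop participation | Stop CBD, follow-up if referred | Both stop product; scope differs |

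The rules differ on stopping in 2 of the 4 cases. The second row is the sharper difference, a stop rule against permission to continue. In the third row one text requires a stop and the other is silent. The unnumbered safety-withdrawal sentence does not fill that gap for an unrelated event, because its adverse-event ground is limited to events associated with the product.

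**Step 4: the cross-reference.** Of the four numbered stopping criteria, 0 name an adverse event. Item 3 is a generic, study-level item. The ground for withdrawing a participant because of an adverse event appears only in the unnumbered sentence above the list. That sentence has no severity threshold, whereas the general rule in the same section applies from moderate upwards.

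**The case against.** The best defence is that the two texts run in parallel. Nothing in the suicidality paragraph suspends physician triage, and its wording on continuing is permissive. It can be read as an immediate crisis step, with the general rule still stopping a related, moderate event. The end-of-study look at relatedness could likewise be an overall review added to the judgement made at the time. This reading is possible, but the protocol does not state it. The opposite reading, that the specific paragraph overrides the general rule, is equally open, and would require an exception in the general rule. Either way new wording is needed.

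Three stronger readings are tempting, and the documents do not support them.

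- *That the texts conflict on who judges relatedness.* The named interviewers assess intent, not relatedness. The relatedness sentence says only that the team will assess it, which may include the study physician, and the interviewer whose name is removed could be that physician. What can be said is that the paragraph does not assign relatedness to the physician.
- *That a signal would be examined only after other participants had finished dosing.* All adverse events go to the IRB within 24 to 48 hours, and the Data and Safety Monitoring Plan provides quarterly team meetings on safety issues. The end of the study may also mean the participant's own end.
- *That the protocol has no safety ground for withdrawal.* It has one, directly above the list. Its lack of a severity threshold need not contradict the general rule, since a discretionary withdrawal can sit beside a required stop.

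That such events are expected to be uncommon is no answer, because the rule has to be clear when one occurs.

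**Conclusion.** The point holds as an unresolved inconsistency on two matters: whether the participant continues, and when relatedness is judged. It has no numeric size. The two rules lead to different stopping outcomes in two of the four combinations of intent with related-and-moderate-to-severe status, and the protocol gives no precedence. The stopping-list fault is a separate and lesser cross-reference defect.

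The conclusion assumes that the checklist given to participants carries the items of the printed list, and that no text outside the document sets an order between the rules. Sample size and analysis are unaffected. Because the gap bears on whether a participant stays on product, it should be corrected and not left to interpretation. This review takes no position on which rule is clinically right.

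**What to change.** Reconcile three passages: the general rule under Safety Monitoring and Stopping Criteria, the suicidality paragraph, and the passive-surveillance paragraph. The protocol should state:

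1. which rule governs suicidal thoughts and ideation, or that both apply and how they combine;
2. when relatedness is judged for these events.

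Then make the Stopping Criteria list consistent with the safety-withdrawal sentence and with the adverse-event rule that refers to it. The content of the rule is for the investigator and the IRB to decide.

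The cost is a few sentences of protocol wording and a short IRB amendment. Visits, samples and analysis do not change.
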